2.0 Objectives*

2.1 The goal of this project is to assess the preliminary feasibility, acceptability, and efficacy of self-administered preoperative tDCS+MBI in older adults (50+) undergoing TKR. The central hypothesis is that combined preoperative tDCS+MBI will decrease postoperative analgesic consumption, postoperative clinical pain severity, as well as preoperative pain-related cortical response. We will accomplish three aims using a randomized controlled trial.

2.2 *Hypotheses:*

To determine the effects of 5, 20-minute preoperative self-administered tDCS sessions combined with brief MBI on analgesic medication consumption following TKR

Hypothesis 1: participants receiving preoperative active tDCS+MBI will show reduced postoperative analgesic consumption.

To determine the effects of 5, 20-minute preoperative self-administered tDCS sessions combined with brief MBI on postoperative pain severity following TKR

Hypothesis 2: participants receiving preoperative active tDCS+MBI will show reduced postoperative pain intensity and pain interference with physical and emotional function 5 days and 1 month after TKR.

To explore the effects of 5, 20-minute preoperative self-administered tDCS sessions combined with brief MBI on preoperative endogenous pain modulation

PROTOCOL TITLE:

Hypothesis 3: participants receiving preoperative active tDCS+MBI will show improved preoperative endogenous pain modulation.

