17.0 Data Management* and Confidentiality

17.1 The protocol will favor an intention-to-treat approach for the analysis of results.

PROTOCOL TITLE:

Data analysis will be performed with R (Vienna, Austria) version 4.1+. Baseline demographic information will be summarized using descriptive statistics. Continuous variables will be summarized with means and standard deviations. Categorical variables will be summarized with counts, proportions, and medians (interquartile range). The distribution of all variables will be examined before any analysis, using appropriate statistical tests like Shapiro's test for normality checking. If the assumption of normality is not met, equivalent non-parametric approaches or data transformation will be employed. The multiple testing problem will be accounted for using Bonferroni correction. All testing will be two-sided and 0.05 will be used as the familywise significance level. If needed, statistical analysis will also be conducted after controlling for baseline demographics and clinical characteristics (e.g., age, sex, and race).

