For Aim 1, analgesic consumption measured on 3 consecutive days will be summarized into one number for each subject. Two-sample t-test (or non-parametric alternative) will be employed to determine the significance of the difference between the active and the sham tDCS+MBI groups. Multivariate linear regression will be further employed to account for potential confounding factors, including selected baseline demographics and clinical characteristics (e.g., age, sex, race, and body mass index). For Aim 2, we will conduct multivariable regression analysis to compare the change in clinical pain intensity (NRS, BPI, PHQ-4, PCS) from baseline to Day 3 in the postoperative phase after controlling for baseline and other confounding factors (e.g., age, race, sex, baseline NRS, consumption of pain medications). We will also determine whether the improvement conferred by active tDCS+MBI can be sustained by comparing the clinical pain intensity changes from baseline to 1 month between the active and the sham groups. We will also conduct sex-stratified analysis and explore whether there exists sex difference in these effects. For Aim 3, the QST dataset for endogenous pain modulation will be analyzed using multivariate linear regression for changes in each of the QST measures against potential confounding factors, and backward stepwise variable selection will then be performed to identify the parsimonious model structures. Spearman rank-order correlation will be used to quantify the association between changes in each of the QST measures and the changes in clinical pain intensity (NRS).

17.2. The PI, RA and research coordinator received the CITI training. Data will be de-identified and a code will be assigned to each participant.

17.3 Data entry will be validated at random.

17.4 Data (questionnaires, sociodemographic and clinical info) will have identifiers removed and banked for a minimum of 3 years per Federal regulations. Deidentified data will be available to research team: PI, co-I ([name] and [name]), RA, statistician ([name], CON). Data will be stored on a password-protected computer. The computer will be stored in a locked room. Any data collected online will be stored on an encrypted data server at the CON. Any downloaded data will be stored on a password protected computer. The RA supervised by the PI will be responsible for data receipt. [name] and [name] will assist with results interpretation.

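### The Aim 3 correlation of QST change with pain change names no arm term; run as written, it can create or inflate an association out of the two arm effects the trial predicts

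*Protocol*

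**What the plan says.** The protocol's analysis text (section 17.1) gives the Aim 3 association in a single sentence: "Spearman rank-order correlation will be used to quantify the association between changes in each of the QST measures" and changes in NRS pain. It names no arm term, by-arm version or partial correlation.

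Nothing nearby supplies one:

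- The Aim 3 regression just before it is described as "multivariate linear regression for changes in each of the QST measures against potential confounding factors". Arm is not named there either.
- The only stratification is by sex, and it follows the Aim 2 text: "We will also conduct sex-stratified analysis and explore whether there exists sex difference in these effects".
- The general adjustment clause is optional and covers baseline variables: "If needed, statistical analysis will also be conducted after controlling for baseline demographics and clinical characteristics (e.g., age, sex, and race").

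Protocol section 2.2 predicts an arm effect on both variables. Hypothesis 2 states that "participants receiving preoperative active tDCS+MBI will show reduced postoperative pain intensity". Hypothesis 3 states that "participants receiving preoperative active tDCS+MBI will show improved preoperative endogenous pain modulation".

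The SAP describes change-score comparisons between groups and mixed models with Condition, Time and their interaction. It does not mention a correlation between QST and pain.

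**The concern.** If treatment improves pain modulation and also lowers pain, arm is a common cause of the two change scores. Active participants then tend to sit at one end of both scales and sham participants at the other. A coefficient over all 40 is non-zero for that reason alone, even if, within each arm, a participant's QST change says nothing about that participant's pain change.

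This is the only planned analysis that links endogenous pain modulation to clinical pain, so a non-zero value invites a mechanistic reading. The coefficient is hardest to interpret in the case the trial hopes for, where treatment works on both.

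**Working it through.** There is no plan figure to reproduce: the documents give no effect size, SD, expected correlation or power for this analysis.

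**Inputs from the documents.** 40 completers (protocol section 12.1) at 1:1 (section 6.1), so 20 per arm. Two-sided testing, 0.05 familywise, Bonferroni (section 17.1). Six QST measures are named in section 4.3: heat threshold, heat tolerance, pressure pain threshold, punctate suprathreshold rating, temporal summation and CPM. That gives an illustrative per-test level of 0.05/6 = 0.0083.

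**Assumptions.** Bivariate normal changes with within-arm SD 1; arm effects dQ on QST (higher is better) and dP on pain, in SD units; within-arm correlation r_w. All values of dQ, dP and r_w are assumed.

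**Step 1: formula.** With equal arms, the arm gap adds dQ²/4 and dP²/4 to the two variances and dQ·dP/4 to the covariance. On the Pearson scale,

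pooled r = (r_w + dQ·dP/4) / √[(1 + dQ²/4)(1 + dP²/4)].

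With r_w = 0, dQ = +d and dP = −d, this is −(d²/4)/(1 + d²/4). For d = 0.8: −0.16/1.16 = −0.14. For d = 1.0: −0.25/1.25 = −0.20.

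**Step 2: false association.** Simulation, 20,000 trials per setting, r_w = 0, both effects in the predicted direction. Repeat runs agree within about one percentage point.

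| d on both changes | Pooled r (formula) | Pooled Spearman, rejection at 0.05 | Pooled, at 0.05/6 | Arm removed, at 0.05 |
|---|---|---|---|---|
| 0.3 | −0.02 | 5% | 1% | 5% |
| 0.5 | −0.06 | 6% | 1% | 5% |
| 0.8 | −0.14 | 14% | 4% | 5% |
| 1.0 | −0.20 | 24% | 8% | 5% |
| 1.2 | −0.26 | 41% | 18% | 5% |

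With arm removed, rejection at 0.05/6 is also nominal, at just under 1%.

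**Step 3: unequal effects.** With dQ = 0.5 and dP = 0, the covariance term dQ·dP/4 is zero; mean rho is 0.00 and rejection 5%. With dQ = 0.8 and dP = −0.3, rejection is 6% to 7%. Material error therefore needs sizeable effects on both variables.

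**Step 4: a real within-arm link.**

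- Same sign as the arm effects (r_w = −0.4, d = 0.8): the mean coefficient is −0.46 pooled against −0.37 with arm removed, and rejection at 0.05 is 87% against about 68%. This is inflation.
- Opposite sign (r_w = +0.4): the pooled mean falls to 0.18 for d = 0.8 and 0.09 for d = 1.0. Power is about 20% and 8%, against 66% to 67% with arm removed. This is masking.
- One effect only (r_w = −0.4, dQ = 0.8, dP = 0): mild dilution, with a pooled mean of −0.35 and power of about 62% against 67%.

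**Step 5: price of adjusting when it was not needed.** With no arm effects and r_w = −0.4, power is about 69% unadjusted and 67% to 68% adjusted.

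**The case against.** Four points on the other side have force.

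- **Pooling is not stated.** A reader might infer that the protocol commits to pooling the arms. It does not; the sentence is silent. Pooling is the natural reading because a Spearman coefficient takes two variables and no covariate, and no by-arm version appears anywhere. So the accurate charge is that the plan does not say how arm is handled, and that carried out literally it pools.
- **Hiding a true association.** A reader might also infer that the effects predicted by Hypotheses 2 and 3 would hide a real association. The documents do not support that. If better modulation goes with less pain within arms, pooling strengthens the association. Masking needs a within-arm link of the opposite sign to the arm effects, and nothing in the documents suggests one.
- **The pooled value is not simply wrong.** If treatment lowers pain through better modulation, part of the between-arm component belongs to that pathway, and removing arm discards it. This stands. But the pooled coefficient cannot tell that pathway from two unrelated arm effects, so it cannot serve alone as the main result.
- **Stakes and thresholds.** Aim 3 is worded as exploratory, the SAP calls pilots hypothesis-generating, and the correlation is absent from the SAP, so it may not have been run. The 0.05 rates are not at the protocol's Bonferroni level, where the absolute rates are lower (about 4% and 8% at d = 0.8 and 1.0), though still above the nominal 0.8%. The SAP drops Bonferroni for its pair-wise comparisons but gives no rule for this correlation. All of this lowers the severity without making the coefficient interpretable.

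**Conclusion.** The point holds in a limited form, at low severity. The Aim 3 correlation has no stated handling of arm. Run as written, it mixes any patient-level link with the product of two arm effects that the trial itself predicts.

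The size depends wholly on assumed effects. The error is negligible up to about d = 0.5 on both changes, material from about d = 0.8 (14% against 5% at the 0.05 level), and absent if only one variable responds. These figures rest on normal data, equal effects on both changes, 20 per arm and no within-arm association.

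One further condition applies. The sentence does not say which NRS change is meant, and Hypothesis 2 concerns postoperative pain, so the predicted arm effect bears most directly on a change from baseline to a postoperative time point.

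**What to change.** - Report as the main Aim 3 association a partial Spearman correlation adjusted for arm: rank both changes, remove the arm means from the ranks, and correlate the residuals on n − 3 degrees of freedom (37 rather than 38 at n = 40). Give a 95% CI.
- Show the two within-arm coefficients beside it.
- If a pooled coefficient is reported, place it next to the adjusted one and label it as including the arm effects.
- State in the SAP whether the correlation is retained, and if so which NRS change it uses.

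The cost is one degree of freedom and one line of analysis. No new data are needed, so it can still be done although the SAP is written in the past tense.

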18.0 Provisions to Monitor the Data to Ensure the Safety of Subjects*

PROTOCOL TITLE:

[name] has the primary responsibility for monitoring study research staff. Research team will receive training on the study design, recruitment and protocol. Weekly meetings will take place with study staff to ensure protocol adherence and monthly meetings with co-investigators to discuss any issues. Patients' experiences and any potential adverse events will be reviewed and discussed. Each treatment session will be remotely supervised via zoom and after each session any potential side effects will be investigated and documented by the research coordinator (see questionnaires), [name]. This monitoring will be continued after surgery for the remainder of the data collection (up to 1 month).

19.0 Provisions to Protect the Privacy Interests of Subjects

- 19.1 *Privacy interest protection is increased by the use of online data collection and intervention tools. Regarding individual interviews, we believe that the questions will not be perceived as intrusive as they only address the intervention and its convenience for patients. However, we will highlight that there is no obligation to answer. Also, if participants prefer not to be recorded, we will take notes on their response and not use the recorder.*
- 19.2 *We will explain to the participants that they can complete questionnaires and strategies at their own pace and that if they feel that a question is making them uncomfortable, they have no obligation to respond.*

20.0 Compensation for Research-Related Injury

- 20.1 *N/A*

21.0 Economic Burden to Subjects

- 21.1 *N/A The intervention is provided remotely. All necessary materials and equipment will be provided. Data collection will be remotely as well. The only time participants will travel to the lab is at the time of the preoperative visit so they can get equipment and baseline data can be collected.*

22.0 Consent Process

- 22.1 *If the patients are interested in participating, A clinician/research coordinator from TOC will introduce the study to potential participants at their preoperative visit by using a flyer, and if the individual agrees to learn more, the PI or RA will enter the room to discuss study, answer questions and have the participant sign the consent*

PROTOCOL TITLE:

*on a printed copy. Once the study team member will have countersigned the consent, a copy will be provided to the participant and a copy will be kept by the study team in a locked cabinet in the PI's office. the *Before any in-person interaction, COVID-19 screening will be conducted.* Although, the PI and RA are fully vaccinated, they will use the CDC self-checker tool and wear a mask at all times. Patients usually receive a COVID screening before starting their visit at the clinic and the clinician will inform them about FSU COVID-19 precautions. An FSU information sheet on FSU COVID-19 precautions will also be distributed at the time of consent.*

We believe that the study will be perceived as being independent from the clinical setting and that participants will not experience undue influence. Moreover, it will be underlined that participating in the study or not will not affect the care they receive.

22.2 *Participants will be adults, not cognitively impaired, who can understand and read English and able to consent. No vulnerable populations will be involved.*

23.0 Process to Document Consent in Writing

23.1 *The consent will be obtained and signed on paper at the preoperative clinic or at the lab baseline visit.*

24.0 Setting

24.1 *Participants will be recruited in the community during their preoperative visit. All intervention and assessment procedures will be performed remotely, online or via telephone, except for the consent and baseline questionnaire (baseline visit) and one follow-up visit before surgery (after the preoperative intervention). Telephone/zoom interviews will be done from [name] lab at innovation park.*

24.2 *The FSU CON is well equipped for any size research project. The CON provides significant research resources for faculty including, 1) computers and computer technical support; 2) day-to-day financial oversight of grants; 3) assistance with financial reporting for project annual and final reports; and 4) consultation on research design, data analysis and dissemination. [name] (PI) maintains individual office in the center. Each office contains a computer and laser printer. The center also houses a research conference room that can be used to meet with members of the research team. Telephone and video-conferencing equipment and programs (i.e., Skype, GoToMeeting) are also available in each of the research team member's offices. Designated office space for federally funded research is available within the TMH Center for Research and Evidenced-Based Practice, in addition to a dedicated*

PROTOCOL TITLE:

file room to store study-related documents and participant files. The College of Nursing provides staff experienced in processing (i.e., collecting, inputting, coding and cleaning) high volumes of data including a dedicated data analyst who works solely on CON research, systems for instrument development and piloting including large scale distribution of surveys, servers and clusters for high demand computing, and network bandwidth to accommodate high volume Internet traffic.

25.0 Resources Available

- 25.1 [name] (TOC) does an average of 4 knee surgeries per week. Considering a potential refusal rate of 30%, it is anticipated that the recruitment will require at least 14 weeks if they meet all criteria.*
- 25.2 A RA will be trained and fully devoted to the project*
- 25.3 Participants are being followed by a team of clinicians (clinic and/or rehab) because of their recent major surgery, thus they have access to medical resources.*

26.0 Multi-Site Research*

This is not a multicenter study.

Study title:

Feasibility, Acceptability, and Preliminary Efficacy of Combined Transcranial Direct Current Stimulation and Mindfulness for Pain After Total Knee Arthroplasty

NCT Number: NCT05673720

Statistical analysis plan

October 10th, 2025

Data analysis was performed with R (Vienna, Austria) version 4.1+. Baseline demographic information was summarized using descriptive statistics. The distribution of all variables was examined before any analysis, using appropriate statistical tests like Shapiro's test for normality checking. If the assumption of normality was not met, equivalent non-parametric approaches were employed. Comparison between groups on changes from baseline in clinical variables as well as effect size (Cohen's d) calculation were conducted using Wilcoxon rank-sum test for score changes with non-normal distribution, and t -test for score changes with normal distribution. Considering the numerous repeated measures and the possibility of imbalances between measures, we conducted an analysis using a generalized mixed effects model to evaluate changes in all outcome measures for both preoperative and postoperative outcomes. Mixed effects models capture more information by offering more flexibility in the presence of missing data and treat time as a continuous variable. Mixed effects models are used for longitudinal observations and are capable of automatically adjusting for baseline differences, accounting for potential confounders (e.g., anxiety) when needed.

For the preoperative period, the analysis looked at differences between preoperative baseline and after 5 sessions with three fixed effects: Condition (Control vs. Treatment), Time (First vs. Last Session) and their interaction Condition*Time to test whether the treatment group showed different patterns of change compared to the control group over time in the preoperative period. For the postoperative period, the analysis looked at differences 1) between Day 1 Post-op vs. Day 5 Post-op, and 2) between Day 1 Post-op vs. 1-month post-op. Our model included three fixed effects: Condition (Control vs. Treatment), Time (Day 1 vs. Day 5 or Day 1 vs. 1-month post-op), and their interaction (Condition*Time) to test whether the treatment group showed different patterns of change compared to the control group over time in the postoperative period.

The significance levels (Type-I error probability) for testing the difference between treatment groups over time was 5% and a p-value less than 0.05 was considered statistically significant. However, this level might seem arbitrary in pilot studies and we considered that in this preliminary study, $p < 0.10$ is suggestive (i.e. a trend) of a significant effect that warrants further study. We did not use any Bonferroni corrections for these pair-wise comparisons since a pilot study is usually designed for hypothesis generation instead of hypothesis testing.

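### The SAP is a past-tense record that departs from protocol 17.1 with no dated account of the changes, so its SAP-only results cannot be presented as pre-specified

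*SAP*

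**What the plan says.** **SAP.** The document is dated "October 10th, 2025" and is in the past tense throughout, starting with "Data analysis was performed with R (Vienna, Austria) version 4.1". It describes two layers of analysis.

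- Changes from baseline in clinical variables are compared between groups by t-test or Wilcoxon rank-sum test, according to normality.
- A mixed model is fitted to all outcomes: "Considering the numerous repeated measures and the possibility of imbalances between measures, we conducted an analysis using a generalized mixed effects model". Its fixed effects are Condition, Time and their interaction. The postoperative contrasts are "between Day 1 Post-op vs. Day 5 Post-op, and 2) between Day 1 Post-op vs. 1-month post-op". Adjustment is described as "accounting for potential confounders (e.g., anxiety) when needed".

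Its final paragraph sets significance at 5%, treats p<0.10 as a trend worth further study, and says that Bonferroni was not used because a pilot generates hypotheses.

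**Protocol 17.1.** This is in the future tense and contains no mixed model.

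- Aim 1: one analgesic total per participant, a two-sample t-test or non-parametric alternative, then a regression adjusted for covariates.
- Aim 2: "we will conduct multivariable regression analysis to compare the change in clinical pain intensity (NRS, BPI, PHQ-4, PCS) from baseline to Day 3", adjusted for baseline and other factors, with the same comparison from baseline to 1 month and a sex-stratified analysis.
- Aim 3: regressions on change in each QST measure with backward selection, and Spearman correlations with change in NRS.
- All aims: two-sided tests, Bonferroni correction, familywise 0.05.

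**The concern.** A document called a statistical analysis plan is normally taken to have been fixed before the results were known. This one was written after the analysis, and it differs from the protocol in model, time reference, adjustment and error control. When two analysis descriptions exist for the same outcomes and only the later one is carried forward, a reader cannot tell whether the choice was independent of the results.

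Two things are at stake. The first is the status of the findings: a mixed-model p-value below 0.05, or below 0.10, could be cited as a planned result and used to justify a larger trial. The second is the question answered. Moving the postoperative reference from baseline to Day 1 changes the treatment contrast itself, not just the method of estimating it.

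**Working it through.** There is no figure in the plan to reproduce. The sample size is 40 completers, with no power calculation. The check is mainly a comparison of the two texts.

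**1. Side by side**

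| Element | Protocol 17.1 | SAP | Traceable to the protocol? |
|---|---|---|---|
| Normality check, non-parametric fallback | Yes | Yes | Yes |
| Two-group t-test or non-parametric test | Aim 1, analgesic total | Change from baseline in clinical variables | Yes in method, though applied to other variables |
| Covariate-adjusted regression | Aims 1, 2 and 3 | Not mentioned; confounders in the mixed model only where needed | No |
| Baseline to postoperative Day 3 | Aim 2 | Not named | No |
| Condition*Time mixed model | Absent | All outcomes | No |
| Postoperative reference | Baseline | Day 1 post-op in the mixed model | No |
| Spearman, QST with NRS | Aim 3 | Not mentioned | No |
| Multiplicity | Bonferroni, familywise 0.05 | Uncorrected 5%, plus p<0.10 | No |

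The schedule in protocol section 4 agrees with 17.1. It places NRS, BPI, PHQ-4 and PCS at baseline, after the sessions, on postoperative Day 3 and at 1 month. It shows none of them on postoperative Day 1.

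**2. What the Day 1 reference does**

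Let T and C be the group means, with subscripts 0 for baseline, 1 for Day 1 and 5 for Day 5.

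- SAP interaction: (T5 − T1) − (C5 − C1).
- Baseline-referenced contrast to the same day: (T5 − T0) − (C5 − C0).

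Suppose the groups are equal at baseline and treatment shifts the mean by δ on both Day 1 and Day 5. The interaction is δ − δ = 0, while the baseline-referenced contrast is δ. All treatment sessions take place before surgery, so an effect already present on Day 1 is plausible. The interaction does not capture it.

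**3. Illustration: two analyses per outcome**

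Assumptions, none from the documents: both analyses are run, the more favourable is reported, and under the null the two statistics are bivariate normal with correlation ρ. The chance of at least one rejection is 1 − P(|Z1| < z and |Z2| < z), with z = 1.960 at 5% and 1.645 at 10%.

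| ρ | Nominal 5% | Nominal 10% |
|---|---|---|
| 0.5 | 9.1% | 17.6% |
| 0.9 | 7.0% | 13.6% |

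This is for one outcome. The Aim 2 regression and the SAP interaction use different time contrasts, so the true correlation is unknown and could lie outside this range.

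**4. Illustration: dropping Bonferroni**

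The number of tests k is not stated. For k independent tests the familywise error is 1 − (1 − α)^k.

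| k (assumed) | Bonferroni, 0.05/k each | Uncorrected 5% | p<0.10 |
|---|---|---|---|
| 4 | 0.049 | 0.185 | 0.344 |
| 10 | 0.049 | 0.401 | 0.651 |
| 20 | 0.049 | 0.642 | 0.878 |

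The outcomes here are likely to be positively correlated, which would lower the last two columns.

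**The case against.** A reader might infer that the mixed model was chosen because of what the data showed. The text does not support that. The stated reason is the number of repeated measures, which the protocol fixed at four time points, and a possibility of imbalance, which is an anticipated problem. The next sentence is a general remark on the method: "Mixed effects models capture more information by offering more flexibility in the presence of missing data and treat time as a continuous variable". No observed imbalance, missingness or result is cited. The open-ended confounder wording leaves discretion, but 17.1 has a similar conditional clause for covariate control.

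A reader might also infer that nothing in the SAP was planned, or that every SAP-only analysis was chosen after data collection. Neither is established. The t-test/Wilcoxon comparison and the normality rule come from the protocol, and the SAP adds a model alongside them. No data-lock date, unblinding date or SAP version history is available, so a past-tense write-up could describe decisions made earlier.

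The SAP is also open about its aims. It calls the study preliminary and hypothesis-generating, never calls the mixed model pre-specified, and states its 5% level. That limits the harm and is a fair argument for relaxing Bonferroni. It does not turn an analysis absent from the protocol into a planned one, and the SAP still declares significance at 0.05 and uses p<0.10 to support further work.

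Finally, 17.1 is not fully determinate. Covariates are given as examples, and 17.1 summarises 3 days of analgesic use where sections 4.2 and 6.2 specify 5. This objection stands, and the fix has to allow for it.

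**Conclusion.** The point holds as one about status and reporting. The SAP was written after the analysis and departs from protocol 17.1 in model, postoperative reference, adjustment and error control. Because neither document says when or why each change was made, or whether unblinded data had been seen, the mixed-model, Day 1-referenced and p<0.10 results cannot be presented as pre-specified. Results from the elements that match the protocol can.

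The most substantive departure is the Day 1 reference, because a treatment difference already present on Day 1 drops out of the interaction. That follows from algebra and needs no assumption about motive.

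The size of any selection bias is unknown. The 7.0% to 9.1% and 13.6% to 17.6% figures depend on an assumed correlation and an assumed choice of the better result. The familywise figures depend on an assumed number of independent tests. None of them estimates what happened in this trial.

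**What to change.** 1. Run the analyses of protocol 17.1, including baseline-referenced change, the adjusted regressions, the Spearman correlations and the Bonferroni-corrected familywise 0.05 level. Report them as the protocol-specified results.
2. Report the mixed-model, Day 1-referenced and p<0.10 results under the label: not in the protocol, exploratory.
3. Add a table with one row per departure, giving its date, its reason and whether unblinded data had been seen. If a change preceded unblinding, this lets the sponsor show it.
4. Where 17.1 leaves a choice open, such as the covariate set or 3 versus 5 days of analgesic data, state the choice made and show the alternative. If Day 3 pain ratings were not collected, say so and identify the baseline-referenced contrast used instead.

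**Cost.** No new data collection is needed if the Day 3 ratings exist. The extra work is more than a handful of models, because 17.1 covers several pain and mood scales at two postoperative times, sex strata and every QST measure. The mixed-model findings become explicitly exploratory, which is consistent with the SAP's own description of the study.

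### The SAP's two-time-point mixed model and its change-score tests do not adjust the treatment contrast for baseline, although the SAP implies that mixed models do so automatically

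*SAP*

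**What the plan says.** The SAP's opening paragraph sets out two between-group analyses.

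- The first is a "Comparison between groups on changes from baseline in clinical variables", done with a "Wilcoxon rank-sum test for score changes with non-normal distribution, and t -test for score changes with normal distribution". No covariate is named.
- The second is a generalized mixed effects model, with no link function stated. Among the reasons given is that such models are "capable of automatically adjusting for baseline differences", with confounders such as anxiety taken into account where required.

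The next paragraph specifies the preoperative model. On time points, "the analysis looked at differences between preoperative baseline and after 5 sessions". The terms are "three fixed effects: Condition (Control vs. Treatment), Time (First vs. Last Session) and their interaction Condition*Time". No term is the outcome's baseline value, and nothing constrains the two arms to a common baseline mean.

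Protocol 17.1 planned differently for Aim 2. The change in NRS, BPI, PHQ-4 and PCS to postoperative Day 3 was to be compared by regression "after controlling for baseline and other confounding factors", with baseline NRS among the examples, followed by a comparison of changes to 1 month. For Aim 3 (preoperative QST) it planned regression of changes on potential confounders and did not name baseline QST. The schedule in Protocol 4.0 places the four Aim 2 measures at baseline and after the fifth session too, so they also fall within the SAP's preoperative model.

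**The concern.** A reader of the SAP would take it that chance baseline differences are dealt with by the choice of model. In the model as listed they are not. The Condition term lets the arms start at different levels, but the interaction then measures the difference in change from those different starts. An arm that happens to start higher tends to fall more through regression to the mean, and that fall is credited to treatment (or, in the other direction, hides an effect).

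With about 20 per arm such imbalances are not small. The SAP's closing paragraph treats p below 0.10 as a trend worth following up, so modest shifts can change which outcomes are carried into the next study. The baseline values that would remove the problem are already collected before randomisation (Protocol 6.1).

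**Working it through.** **Inputs from the documents.** 40 completers (Protocol 12.1) and 1:1 allocation (Protocol 6.1), so n = 20 per arm and N = 40; two-sided testing (Protocol 17.1) at 5% (SAP). The plan states no power, SD, effect size or correlation, so there is no figure of its own to reproduce.

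**Assumptions.** Equal SDs at both times, scaled to 1; correlation ρ between baseline and follow-up of 0.3, 0.5, 0.7 and 0.9; an illustrative effect of 0.8 SD.

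**Step 1: what the interaction estimates.** With two time points and complete data, the Condition*Time coefficient is (follow-up mean − baseline mean) in the active arm minus the same difference in the sham arm, which is the difference in mean change. On simulated data with 20 per arm, a linear random-intercept model fitted by REML and the change-score t-test gave the same t: −2.478 and −2.478 (ρ = 0.3), −2.857 and −2.857 (ρ = 0.6), −2.397 and −2.397 (ρ = 0.8). ANCOVA on the same data gave −2.720, −2.674 and −1.918, so it is a different analysis.

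**Step 2: precision.** Per-patient variance is 2(1 − ρ) for change and 1 − ρ² for ANCOVA. Estimating the ANCOVA slope multiplies the variance of its contrast by 1 + 1/(N − 4) = 1 + 1/36 = 1.028. Each SE is √(variance × 2/20). Power uses the non-central t on 38 df (change) and 37 df (ANCOVA).

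| ρ | Change variance | ANCOVA variance × 1.028 | Ratio change/ANCOVA | Reduction | SE change | SE ANCOVA | Power at 0.8 SD, change | Power at 0.8 SD, ANCOVA |
|---|---|---|---|---|---|---|---|---|
| 0.3 | 1.40 | 0.935 | 1.50 | 33% | 0.374 | 0.306 | 55% | 72% |
| 0.5 | 1.00 | 0.771 | 1.30 | 23% | 0.316 | 0.278 | 69% | 80% |
| 0.7 | 0.60 | 0.524 | 1.15 | 13% | 0.245 | 0.229 | 89% | 93% |
| 0.9 | 0.20 | 0.195 | 1.02 | 2% | 0.141 | 0.140 | over 99% | over 99% |

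Simulation at 20 per arm agrees with these ratios and powers to within simulation error. For an assumed 0.5 SD effect, simulated power was 25% against 35%, 34% against 42%, 52% against 57%, and 93% against 94% at the four correlations.

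**Step 3: effect of a chance imbalance.** Given a baseline difference D between arms, the change-score contrast is shifted by −(1 − ρ)D. One SE of imbalance is √(2/20) = 0.316 SD, so the size of the shift is:

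- ρ = 0.3: 0.7 × 0.316 = 0.22 SD
- ρ = 0.5: 0.5 × 0.316 = 0.16 SD
- ρ = 0.7: 0.3 × 0.316 = 0.09 SD
- ρ = 0.9: 0.1 × 0.316 = 0.03 SD

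The simulated slopes of the change-score estimate on D were −0.70, −0.50, −0.30 and −0.09; for ANCOVA they were about 0.

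**Step 4: unconditional bias.** Averaged over simulated randomisations with a true effect of 0.50, both estimators had a mean of about 0.50.

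**The case against.** Several points on the other side stand and limit the finding.

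- **The inference is not invalid.** A reader might infer that the SAP's results are biased. Over randomisation they are not; the bias is conditional on the imbalance that happened to occur.
- **ANCOVA is not always the more precise.** Once the slope has to be estimated from 40 patients, the variance ratio is 1.02 at ρ = 0.9 and falls just below 1 at 0.95. In single data sets ANCOVA's SE was the larger in about 14% of simulated trials at ρ = 0.7 and in nearly half at 0.9.
- **The SAP sentence is about a class of models.** It says what mixed models are capable of, and one with baseline means constrained equal does adjust. That defends the class, but the model listed carries no such constraint.
- **The protocol contrast is narrow.** It is tempting to say that a promised adjustment was dropped for every preoperative outcome. The promise covers the Aim 2 measures, with Day 3 and 1 month as its named time points. No such promise was made for preoperative QST.
- **The equality in Step 1 has conditions.** With missing values or a non-Gaussian link it is only approximate.
- **The stakes are those of a pilot.** The Study Summary gives feasibility and acceptability as the primary objective, and the SAP regards the work as hypothesis-generating. Analgesic consumption, the primary endpoint in Protocol 4.2, is scheduled only after surgery, so it has no baseline value to adjust for and this point does not reach it.

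None of this supplies the missing adjustment. Nothing elsewhere in either document puts the outcome's baseline value into the SAP's analyses.

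**Conclusion.** The concern holds in a limited form. As listed, the preoperative mixed model and the change-from-baseline tests leave the treatment contrast unadjusted for the outcome's baseline value, so the automatic-adjustment sentence is not true of that model. For NRS, BPI, PHQ-4 and PCS the SAP also departs from the baseline control planned in Protocol 17.1.

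The cost is precision, together with sensitivity to chance imbalance. It is material at correlations of 0.3 to 0.5, modest at 0.7 and negligible near 0.9. Where in that range each outcome falls cannot be settled from the documents. The figures assume equal SDs, complete data on 20 per arm and a linear model; the powers also assume a 0.8 SD or 0.5 SD effect. This should be corrected, but it does not invalidate the trial's comparisons.

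**What to change.** For every outcome with a pre-randomisation value, covering both the preoperative outcomes and the change-from-baseline comparisons, regress the follow-up value on arm plus that outcome's baseline value, using rank ANCOVA where the distribution is non-normal. A mixed model with baseline means constrained equal across arms is an acceptable alternative.

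The SAP is written in the past tense about analyses already done, so report these results beside the existing ones and label them post hoc; do not substitute them silently. Note that for the Aim 2 measures they restore the baseline control the protocol had planned. Reword the SAP sentence to say that the model as fitted does not adjust the contrast for baseline, and that the added analysis does. Leave analgesic consumption out of this change.

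The cost is one degree of freedom per model (38 to 37), a re-run on data already collected and a short edit to the SAP.
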